**10.9. Appendix 9: Abbreviations**

AASLD	American Association for the Study of Liver Diseases
AAV	adeno-associated virus vector
AAV2	adeno-associated virus vector, serotype 2
AAV8	adeno-associated virus vector, serotype 8
AAV-hFIX	adeno-associated viral vector expressing human factor IX
AAV2-hFIX16	single-stranded adeno-associated viral vector, serotype 2, expressing human factor IX under control of the human $\alpha$ 1-antitrypsin promoter coupled to the human apolipoprotein E hepatic locus control region
AAV8-hFIX19	single-stranded adeno-associated viral vector, serotype 8, expressing human factor IX under control of the human $\alpha$ 1-antitrypsin promoter coupled to the human apolipoprotein E hepatic locus control region (construct changes from hFIX16 to hFIX19 include codon-optimization, removal of alternate open reading frames of the factor IX gene, and replacement of amp with kan resistance in the plasmid used for vector generation)
AAV8-LP1-hFIXco	self-complementary AAV vector, serotype 8, expressing human factor IX, used in the St. Jude's/UCL gene therapy trial
AAV-Spark100-hFIX19-Padua	adeno-associated viral vector comprised of the Spark100 AAV capsid encoding hFIX-Padua
ABR	annualized bleed rate
AEs	adverse events
AIDS	acquired immunodeficiency syndrome
ALT	alanine aminotransferase
amp	ampicillin resistance gene
APRI	AST-to-platelet ratio index
aPTT	activated partial thromboplastin time
AST	aspartate transaminase
BMI	body mass index
BUN	blood urea nitrogen
CFR	Code of Federal Regulations
CNS	central nervous system
cp	capsid particles
CPT	common protocol template
CRO	Contract Research Organization

CSR	clinical study report
CT	clinical trial
CTL	cytotoxic T lymphocyte
CVAD	central venous access device
DNA	deoxyribonucleic acid
DMC	data monitoring committee
DILI	drug-induced liver injury
DRE	disease related event
EAHAD	European Association for Haemophilia and Allied Disorders
eCRF	electronic case report form
ECG	electrocardiogram
ED	exposure day
EDP	exposure during pregnancy
ELISPOT	enzyme-linked immunospot assay
EOS	end of study
EudraCT	European Clinical Trials Database
FDA	Food and Drug Administration
FIX	factor IX
FIX:C	Circulating factor IX
GCP	Good Clinical Practice
GGT	gamma-glutamyl transferase
Haem-A-QoL	haemophilia A quality of life questionnaire
HAL	hemophilia activities list
HBV	hepatitis B virus
HBsAg	hepatitis B surface antigen
HCV	hepatitis C virus
hFIX	human coagulation factor IX
HIV	human immunodeficiency virus
HJHS	hemophilia joint health score
HLA	human leukocyte antigen
HRQoL	health-related quality-of-life
IB	Investigator Brochure
ICF	Informed Consent Form
ICH	International Council for Harmonisation
ID	Identification
IEC	independent ethics committee
IFN	interferon
IFN- $\gamma$	interferon gamma
IgG4	immunoglobulin G subclass 4
IND	investigational new drug
INR	international normalized ratio
IP	investigational product
IRB	institutional review board
ISF	investigator site file

IU	international units
IV	intravenous
kan	kanamycin resistance gene
LDH	lactate dehydrogenase
LFT	liver function test
LSLV	last subject last visit
LTFU	long-term follow-up
MHC	major histocompatibility complex
NAb	neutralizing antibody
NHP	non-human primate
PBMC	peripheral blood mononuclear cells
PCD	primary completion date
PCR	polymerase chain reaction
pd	plasma derived
pd-FIX	plasma-derived factor IX
PK	pharmacokinetic
PO	orally
PT	prothrombin time
QD	once a day
QoL	quality of life
rFIX	recombinant factor IX
RNA	ribonucleic acid
ROTEM	rotational thromboelastogram
SAE	serious adverse event
SAP	statistical analysis plan
SJ-UCL	St. Jude Children's Research Hospital – University College London
SOP	standard operating procedure
PF-06838435	adeno-associated viral vector with FIX gene (AAV-Spark100-hFIX19-Padua)
SUSAR	suspected unexpected serious adverse reaction
TAT	thrombin-antithrombin
TBili	total bilirubin
TEG	thromboelastography
TGA	thrombin generation assay
T max	Time at maximum activity
ULN	upper limit of normal
vg	vector genome
WBC	white blood cell
WNL	within normal limits
WT	wild-type

---

Hemophilia B, or Christmas disease, is a rare congenital bleeding disorder characterized by the deficiency of blood coagulation factor IX (FIX). Individuals with hemophilia B often experience mild-to-severe bleeding complications and it can be life-threatening if not treated appropriately. There is no available cure for hemophilia B. Prophylaxis, with regular infusion of FIX concentrates, is now the mainstay of hemophilia care to resolve bleeding episodes (episodic treatment) or prevention of bleeding (prophylaxis treatment) (Roberts and Eberst 1993; Srivastava et al. 2012; National Hemophilia Foundation 2007).

Over the past two decades, a series of preclinical and early-phase clinical studies on gene transfer for hemophilia have demonstrated a good safety profile using adeno-associated viral (AAV) for hemophilia B. Recent success reported by Nathwani et al., (2011 and 2014) of sustained long-term expression (up to 6 years) of therapeutic levels of FIX between 2% and 6% activity levels in subjects with severe hemophilia B using AAV serotype 8 (AAV8) liver-directed gene transfer further validated the potential of gene transfer technology.

PF-06838435 is an adeno-associated viral (AAV) vector expressing the human factor IX-Padua (hFIX-Padua) variant. PF-06838435 is being administered for the first time to humans; however, AAV vectors have been administered to humans in more than 100 gene therapy clinical trials for a wide range of indications, including hemophilia B (Nathwani et al. 2014; Buchlis et al. 2012; Mingozzi and High 2013; Mingozzi and High 2011b; High and Aubourg 2011).

Protocol number was changed to C0371005 (formerly SPK-9001-101) after Investigational New Drug (IND) transfer from Spark Therapeutics to Pfizer Inc on July 11, 2018.

2. Objectives

2.1. Primary and Secondary Objectives

The primary objective of the study is to evaluate the safety and tolerability of a single intravenous infusion of PF-06838435 in hemophilia B subjects ≥ 18 years of age with ≤ 2 IU/dL [$\leq 2\%$] endogenous factor IX [FIX]). The secondary objective is to characterize the kinetics of PF-06838435.

3. Investigational Plan

3.1. Overall Study Design and Plan

This is a Phase 1/2a, open-label, non-randomized, dose-escalation and multi-center study to evaluate the safety, tolerability, and kinetics of a single intravenous infusion of PF-06838435 in hemophilia B subjects with ≤ 2 IU/dL [$\leq 2\%$] endogenous factor IX [FIX]).

Approximately 15 evaluable subjects will be dosed with a single intravenous infusion of PF-06838435 at one of three different dose levels.

Subjects will provide informed consent and then undergo screening assessments up to 6 (± 2) weeks prior to PF-06838435 infusion on the Dosing Day (Day 0). All dosed subjects will undergo safety observation for a total of 52 (± 2) weeks after PF-06838435 infusion (see the Schedule of Events). Subjects who complete 52 (± 2) weeks (End-of-Study) will be encouraged to enroll in an extension study evaluating the long-term safety of PF-06838435 for up to an additional 5-year long-term follow-up (LTFU).

The administration of PF-06838435 to the first two subjects in the starting dose level will be staggered by at least two (2) weeks to ensure safety. Additionally, at least eight weeks of safety data from at least three (3) out of five (5) subjects in a given dose level will undergo review by an independent Data Monitoring Committee (DMC) prior to dosing the first subject in the next dose level.

There will be no dose escalation if at least three (3) subjects in any dose level achieve steady-state vector-derived FIX activity levels of $\geq 40\%$. Steady-state levels are based on an average of vector-derived FIX:C activity level measurements starting from Week 12 with adequate washout (i.e., 96 hours for pd- or r-FIX and up to 168 hours for extended half-life rFIX) from FIX product.

Originally, up to five (5) evaluable subjects may be dosed in each dose level. An initial dose level may be expanded up to ten (10) evaluable subjects if at least three (3) out of five (5) subjects achieve detectable steady-state vector-derived FIX activity levels above 5%. If, after the above initial dose-level expansion, at least six (6) out of ten (10) subjects achieve detectable steady-state vector-derived FIX activity levels above 5%, then further dose level expansion of up to ten (10) additional evaluable subjects would be allowed (a total of up to twenty evaluable subjects at the starting dose level of 5×10^{11} vg/kg).

The decision to dose escalate will require the agreement of the Sponsor and the DMC.

CCI
[Redacted text block]

3.2. Study Endpoints

3.2.1. Primary Endpoints

- Clinically significant changes from baseline in the following:
 - Physical examination
 - Vital signs

- Laboratory values
 - Incidence of drug-related adverse events (including inhibitor development)
 - FIX incremental recovery
 - Immune response against AAV capsid protein
- Laboratory parameters of thrombotic potential in any individual who reaches >150% vector-derived FIX:C activity levels after PF-06838435 infusion.

3.2.2. Secondary Endpoints

- Characterization of PF-06838435 kinetics, including:
 - Vector-derived FIX:C activity levels:
 - Peak
 - Steady-state
 - FIX antigen levels

3.3. Study Drug Dosing

The study will consist of the following phases (See Appendix 1 Study Schematic):

- Screening period (up to 6 [±2] weeks);
- Dosing day (Day 0);
- Safety observation period (52 [±2] weeks post-infusion of PF-06838435).

The total duration of the study per subject is approximately 58 weeks (including up to 6 weeks of screening).

Subjects should be reminded to have washout of at least 96 hours (4 days) without FIX protein product or longer washout for extended half-life FIX protein product prior to any blood draw and infusion on Day 0.

Subjects will receive a bolus infusion of FIX protein product for FIX incremental recovery followed by a single intravenous infusion of PF-06838435 on Dosing day (Day 0). The complete dose of PF-06838435 will be infused via infusion pump over a period of up to 60 minutes under medical supervision.

4. General Statistical Considerations

In general, the following rules will be followed for all applicable analyses contained in this analysis plan, unless otherwise specified. Analysis populations used in specific analyses will be noted in the tables/listings.

Continuous variables will be summarized using descriptive statistics including: the number of non-missing values, mean, standard deviation, median, minimum and maximum. Means and medians will be presented to one decimal place beyond that which the data was captured. Standard deviations (SD) will be presented to two decimal places beyond that which the data was captured. Minimum and maximum will be displayed to the same number of decimal places as that which the data was captured. In case of non-normally distributed variables (such as some laboratory parameters), the geometric mean may be calculated.

Categorical variables will be summarized by count and percentage. All percentages will be rounded to the nearest integer. The percentage will be suppressed when the count is zero. Unless otherwise specified, the denominator for all percentages will be the number of subjects in each treatment arm with non-missing data for a given summarization.

Baseline will be defined as the last non-missing measurement (that can be used for data analysis) taken prior to PF-06838435 infusion.

Study day, that is the start/stop date of an event, will be calculated as (date of event – first PF-06838435 infusion date) if event date is prior to PF-06838435 infusion date; Study Day will be calculated as (date of event – first PF-06838435 infusion date+1) if event date is on or after PF-06838435 infusion date.

Unscheduled visits will not be included in table summaries but will be included in the data listings.

Handling of incomplete or missing data:

No imputation will be applied for missing data for the analyses of safety or efficacy endpoints.

Data presentations:

Disposition and safety analyses will be presented for all subjects. All efficacy analyses will be presented overall and by regimen (prophylaxis and on-demand) as appropriate.

All analyses will be conducted using SAS version 9.2 or higher.

4.1. Sample Size

The sample size is based on the need to establish the initial safety and kinetic profile of PF-06838435. Up to 30 evaluable subjects will be evaluated in the study.

There are no formal statistical hypotheses related to the objectives of the study. Thus, the sample size is based on clinical rather than statistical considerations.

4.2. Randomization and Blinding

This is a non-randomized open-label study.

4.3. Analysis Set

4.3.1. Safety Analysis Set

The safety analysis set is defined as all subjects who receive the infusion of PF-06838435. The analysis of safety and efficacy will be performed in this population.

4.3.2. All-Enrolled Analysis Set

The all-enrolled analysis set is defined as all subjects who signed informed consent. Subject disposition will be reported in this population.

4.3.3. Pharmacokinetics (PK) Analysis Set

The PK analysis set will include subjects who have received PF-06838435 and have collected vector-derived FIX:C activity levels enabling acceptable determination of the peak and steady-state derived activity level.

CCI

4.3.5. FIX Incremental Recovery Analysis Set

The FIX incremental recovery analysis set will include subjects who have received 100 IU/kg of FIX protein product infusion and have completed a blood sample collection

within the first 3-hours post infusion for FIX protein product enabling determination of FIX incremental recovery. The FIX incremental recovery analysis set will be used for the summary of FIX incremental recovery described in Section 10.1.

5. Subject Disposition

5.1. Disposition

Subject disposition will be summarized by dose group for all subjects in the all-enrolled analysis set. This table will present the count and percentage of subjects in each analysis set as defined in Section 4.3, number screen-failed, number completed, and number discontinued by primary reason. The duration on study (date of withdrawal or completion – date of PF-06838435 infusion + 1) will be summarized by dose group with descriptive statistics. A data listing will be provided along the disposition table.

5.2. Protocol Deviations

Protocol deviations/violations will be presented in a data listing.

5.3. Inclusion and Exclusion Criteria

Any protocol violations regarding inclusion and exclusion criteria will be presented in a listing.

6. Demographics and Baseline Characteristics

6.1. Demographics

Demographic and other baseline characteristics (age, race, ethnicity, weight at screening and height at PF-06838435 infusion day) will be summarized by dose group using the safety analysis set. Age will be calculated as the integer part of (Date of Informed Consent – Date of Birth)/ 365.25. For sites where only year of birth is collected, age will be calculated as (Year of Informed Consent – Year of Birth). Age will be summarized both as a continuous variable and grouped by <35, ≥35 years of age.

A demographic and baseline characteristics data listing will also be provided.

6.2. Medical History

6.2.1. General Medical History

The significant medical and surgical history will be summarized by dose group for each body system, preferred term and presented using the safety analysis set. A subject will be counted only once if the subject reported one or more occurrences in the same body system and preferred term.

A data listing of subjects' medical and surgical history will also be provided for subjects in the safety analysis set, which will include medical condition/surgery hemophilia relatedness, start/stop date and ongoing status of the event as well.

6.2.2. Baseline Hemophilia History and Hemophilia Bleed Treatment History

Hemophilia history at screening including severity criteria, blood type, Rh factor, number of days of exposure to pd-FIX or rFIX product (<50 , ≥ 50), inhibitor history (positive Bethesda titer, Family history of inhibitor), and allergy/anaphylaxis history (any history of Allergic type or Anaphylaxis reactions associated with administration of FIX products) will be summarized by dose group. Detailed data of each subject will be provided in data listings which will also include date of diagnosis, genotype and HLA type.

The annual bleeding rate will be reported as the total number of bleeding episodes in the 52 weeks prior to Screening Visit and will be summarized for prophylactic subjects, on-demand subjects, and overall by dose group.

For prophylactic subjects, number of prophylactic infusions in the past 12 weeks and 52 weeks prior to screening will be summarized by dose group. Number of spontaneous and traumatic bleeds in the same time periods will also be summarized by dose group. For on-demand subjects, the number of traumatic and spontaneous bleeds in the 52 weeks prior to screening will be summarized by dose group.

Prior (26 weeks preceding screening) and current FIX product, treatment regimen, dose, schedule, start and stop date will be also summarized overall, by regimen (Prophylaxis vs. On-demand), and dose group. FIX treatment information will also be presented in listings.

6.2.3. Target Joint History

Target joint (per protocol definition) history (52 weeks preceding screening) collected at screening which includes joint type and symptoms, will be summarized using data from subjects in the safety analysis set and presented by regimen (Prophylaxis vs. On-demand), dose group, and overall. Detailed data of each subject will be provided in data listings which will also include onset date and number of bleeds during the last 52 weeks.

7. Treatments and Medications

7.1. Prior and Concomitant Medications

Prior and Concomitant medications will be summarized separately by anatomical therapeutic chemical, medication names and dose group using the safety analysis set. Prior medications include all medications taken within 30 days prior to screening to the PF-06838435 infusion date.

Concomitant medications are any medication or substance that has a stop date that is on or after the date of PF-06838435 infusion.

Prior and concomitant medication will be coded using WHODRUG version June 1, 2015 (will be updated once per year).

Data on both prior and concomitant medications will be displayed in a data listing. Number of days from infusion of PF-06838435 to the start/stop date of prior or concomitant medication will be included.

Medications with start/stop dates that are partially missing will be analyzed in the summary tables as follows; Original dates will be displayed in the listings.

- If the start date is partially missing: a '01' will be used for the day and 'Jan' will be used for the month
- If the stop date is partially missing: a '28', '29', '30', or '31' will be used for the day (depends on the month and the year) and 'Dec' will be used for the month.

If the start date of a concomitant medication is completely missing, then the therapy will be included in the concomitant medications summary table if the stop date of the medication is on or after the date of PF-06838435 infusion.

An additional listing will be provided for the use of corticosteroids or alternative immunosuppressive therapy in any individual who develops hepatic transaminase elevation of 1.5-fold above baseline or successively increasing over baseline.

7.2. Study Treatments

7.2.1. Extent of Exposure

PF-06838435 infusion information will be summarized in the safety analysis set by dose group. Body mass index (<30 , ≥ 30), duration of infusion, and total dose of PF-06838435 will be summarized. A data listing will be presented along of each subject's infusion information of PF-06838435, including infusion start and stop time.

Coagulation factor IX product administered on Day 0 and Week 52 will be summarized. Summaries will be presented for type of FIX product and FIX product dose at each time point. A listing of the FIX product dosing will also be included.

CCI

CCI [Redacted]

[Redacted]

[Redacted]

[Redacted]

[Redacted]

[Redacted]

[Redacted]

[Redacted]

[Redacted]

[Redacted]

[Redacted]

[Redacted]

CCI [Redacted]

[Redacted]

[Redacted]

[Redacted]

[Redacted]

[Redacted]

[Redacted]

[Redacted]

[Redacted]

[Redacted]

CCI [redacted]
[redacted]
[redacted]
[redacted]
[redacted]
[redacted]
[redacted]
[redacted]
[redacted]

[redacted]
[redacted]
[redacted]
[redacted]
[redacted]
[redacted]
[redacted]
[redacted]
[redacted]
[redacted]
[redacted]
[redacted]
[redacted]
[redacted]
[redacted]
[redacted]
[redacted]

[figure not shown]
[redacted]
[redacted]
[redacted]
[redacted]
[redacted]

[redacted] [redacted]

[redacted]
[redacted]
[redacted]
[redacted]
[redacted]

[redacted] [redacted]

[redacted]
[redacted]

9. Safety Analysis

All safety analyses will be conducted using the safety analysis set.

9.1. Adverse Events

An adverse event (AE) is any untoward, undesired, or unplanned medical occurrence in the form of any unfavorable and unintended sign (including clinically significant abnormal laboratory finding), symptom, or disease temporally associated with the use of the study drug, regardless of causal relationship, occurring in a subject participating in a clinical study. In this study, bleeding episodes are not considered AEs, but bleeding episodes that meet the criteria of serious are to be reported as serious adverse events (SAEs). Adverse events will be classified using the Medical Dictionary for Regulatory Activities (MedDRA) System Organ Classes and Preferred Terms. MedDRA version 18.0 will be used through-out the study.

An adverse event will be regarded as treatment emergent AE (TEAE) if the start date is on or after the infusion of PF-06838435 but before subject's last visit on study (or the date of withdrawal/the date of being lost to follow-up). We will use the below algorithm to derive the start date for the determination of treatment emergence when start date is partially/completely missing and the original dates will be displayed in the listings:

- If year is missing (or completely missing) then set to the PF-06838435 infusion date
- If (year is present, and month and day are missing)
 - If year = year of PF-06838435 infusion date: then set to the PF-06838435 infusion date
 - If year < year of PF-06838435 infusion date: set month and day to December 31st
 - If year > year of PF-06838435 infusion date: set month and day to January 1st
- If month and year are present and day is missing:
 - If year = year of PF-06838435 infusion date, and:
 - month = month of PF-06838435 infusion date: set day to day of SPK-9001 infusion date
 - If month < month of PF-06838435 infusion date: set day to last day of month.
 - If month > month of PF-06838435 infusion date: set day to 1st day of month
 - If year < year of PF-06838435 infusion date: set day to last day of month.

- If year > year of PF-06838435 infusion date: set day to 1st day of month.

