**3. OBJECTIVES, ESTIMANDS AND ENDPOINTS**

Objectives	Endpoints
Primary	

 
The primary objective is to evaluate the safety and tolerability of a single IV infusion of PF-06838435 in hemophilia B participants ≥18 years of age with ≤2 IU/dL [≤2 %] endogenous factor IX [FIX].
 
	
Clinically significant changes from baseline in the following:
 
 
Physical examination
 
Vital signs
 
Laboratory values
 
Incidence of drug-related adverse events (including inhibitor development)
 
FIX incremental recovery (time at maximum activity [Tmax] and percent recovery for FIX activity)
 
Immune response against AAV capsid protein
 
Immune response against hFIX transgene
 
 
For those individuals who develop hepatic transaminases (ALT and/or AST) elevation of approximately 1.5-fold or successively increasing during follow-up above baseline (or vector-derived FIX:C activity levels decline without evidence of FIX inhibitor, accompanied by rising IFN ELISPOTs on PBMCs) after PF-06838435 infusion, treatment with corticosteroids will be instituted. Alternative immunosuppressive

	
therapies will be considered if the initial corticosteroid treatments are not successful.
 
For any individual who reaches >150% vector-derived FIX:C activity levels after the infusion of PF-06838435, laboratory parameters of thrombotic potential will be assessed.

Secondary	

• The secondary objective is to characterize the kinetics of PF-06838435.

	

• Vector-derived FIX:C activity levels:

• Peak

• Steady-state

• FIX antigen levels

CCI
 	

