### **8.3.6. Disease-Related Events and/or Disease-Related Outcomes Not Qualifying as AEs or SAEs**

The disease related events (DREs) for this study include episodes of bleeding related to hemophilia B. The bleeding episode itself is not reported as an AE, unless the bleeding episode meets the criteria outlined below.

Consideration on whether the bleeding event is a DRE is based on investigator determination and bleeding events recorded by the participant in their electronic diary will be reviewed by the investigator and assessed against reporting obligations for S/AE.

Bleeding, not due to the participant's hemophilia, will be recorded as an AE, and not a DRE.

If any of the following conditions apply, then the event must be recorded and reported as an AE or SAE (instead of a DRE):

- Bleeding events that require hospitalization or meet other SAE criteria ([Section 10.3](#)) should be reported as SAEs. When bleeding episodes that meet the SAE criteria are recorded on the AE CRF, the location (site) of the bleed and the etiologic classification as spontaneous or traumatic should be included.
- The bleeding event is, in the investigator's opinion, of greater intensity, frequency, or duration than expected for the individual participant.

OR

- The investigator considers that there is a reasonable possibility that the bleeding event was related to study intervention.

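### SAP 9.1 treats bleeds as AEs only when serious, contradicting protocol 8.3.6 and, applied as written, keeping non-serious related bleeds out of the drug-related AE tables

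*SAP*

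**What the plan says.** Protocol 8.3.6 treats a hemophilia bleed as a disease-related event (DRE) by default: "The bleeding episode itself is not reported as an AE, unless the bleeding episode meets the criteria outlined below". It then sets conditions, any one of which is enough: "If any of the following conditions apply, then the event must be recorded and reported as an AE or SAE (instead of a DRE". There are three:

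- Seriousness: "Bleeding events that require hospitalization or meet other SAE criteria".
- Worse than expected: "The bleeding event is, in the investigator's opinion, of greater intensity, frequency, or duration than expected for the individual participant".
- Relatedness: "The investigator considers that there is a reasonable possibility that the bleeding event was related to study intervention".

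It separately provides: "Bleeding, not due to the participant's hemophilia, will be recorded as an AE, and not a DRE".

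SAP 9.1 covers the subject in one sentence: "bleeding episodes are not considered AEs, but bleeding episodes that meet the criteria of serious are to be reported as serious adverse events". Only seriousness survives from the protocol's conditions.

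Both documents make drug-related AEs part of the primary endpoint. Protocol section 3 lists "Incidence of drug-related adverse events (including inhibitor development", and SAP 3.2.1 repeats it.

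**The concern.** The two documents define different sets of events under the same name. A non-serious bleed that the investigator considers possibly related must be recorded as an AE under the protocol, yet is not an AE under the SAP. The SAP tables that report drug-related AEs are built from treatment-emergent AEs, so an event that fails the SAP definition has no route into them.

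Such bleeds are plausible here. Participants are asked to stop routine prophylaxis after the vector infusion (protocol 6.5.1 and the Schedule of Activities notes), and the investigator must assess diary-recorded bleeds against the AE reporting rules (protocol 8.3.6).

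The direction also matters. Elsewhere the SAP resolves doubt towards more reported harm: a missing relationship is tabulated as related (9.1.2), a missing severity as severe (9.1.3) and a missing toxicity grade as Grade 4 (9.1.4). The bleed sentence works the other way.

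**Working it through.** There is no sample size, power or error rate to reproduce: the study tests no formal hypothesis (protocol 9.1.2). The check is a comparison of texts, followed by a simple calculation of size.

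**Step 1. The two rules side by side.**

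| Type of bleed | Protocol 8.3.6 | SAP 9.1 as written |
|---|---|---|
| Hemophilia bleed meeting no condition | DRE, not an AE | Not an AE |
| Serious | SAE | SAE |
| Non-serious, worse than expected, judged unrelated | AE | Not an AE |
| Non-serious, reasonable possibility of relatedness | AE | Not an AE |
| Non-serious, not due to hemophilia | AE | Depends on what the SAP means by bleeding episodes |

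The documents agree on the first two rows and contradict each other on the third and fourth. The fifth is ambiguous.

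**Step 2. Which outputs are affected.**

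- Row 4 affects the relationship summary (SAP 9.1.2, Table 14.3.1.4) and the drug-related TEAE table (Table 14.3.1.2), and so the primary endpoint. It also affects the overall TEAE tables.
- Row 3 affects the overall TEAE, severity and toxicity-grade tables (SAP 9.1.1, 9.1.3, 9.1.4), but not the drug-related incidence.

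**Step 3. Direction.** The SAP rule adds no class of bleed to the protocol's list and removes at least two. The denominator is the number of participants in the dose group in the safety set (SAP 9.1.2), which does not depend on how bleeds are classified. Incidence can therefore only stay the same or fall.

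**Step 4. Size per participant.** SAP 9.1.1 counts a participant once per level of summary. If x of n participants have a drug-related TEAE, and for one of them the only such event is an omitted bleed, incidence changes from x/n to (x − 1)/n, a fall of 1/n.

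| n | Source of n | Fall, percentage points |
|---|---|---|
| 5 | Initial size of a dose level (protocol 4.1.3.1) | 1/5 = 20 |
| 10 | First expansion (protocol 4.1.3.1) | 1/10 = 10 |
| 15 | Approximate total (SAP 3.1) | 1/15 = 6.7 |
| 20 | Approximate total (protocol 9.2); cap after further expansion of a dose level (protocol 4.1.3.1) | 1/20 = 5.0 |
| 30 | Upper limit (SAP 4.1) | 1/30 = 3.3 |

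If that participant has another drug-related TEAE, overall participant-level incidence does not change. The event count would still be one lower, and the bleed would still be missing from its own system-organ-class and preferred-term row.

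**Step 5. Illustration with assumed counts.** Suppose that one of 20 participants has a drug-related AE and that it is a non-serious bleed. With exact (Clopper-Pearson) 95% intervals:

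- Protocol rule: 1/20 = 5.0% (0.1 to 24.9).
- SAP rule: 0/20 = 0% (0 to 16.8). The upper limit is 1 − 0.025^(1/20) = 0.168.

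The documents give no expected number of such bleeds, so this shows scale only and is not a forecast.

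**The case against.** The strongest reply is that nothing would be lost in practice. The SAP sentence sits in a definitional paragraph and is not a derivation rule. No visible SAP text tells a programmer to find bleeds on the AE page and remove them. Sites following the protocol will record the qualifying bleeds as AEs, SAP 9.1.1 lists all AEs, and SAP 9.1.2 tabulates them by the investigator's assessment of relationship.

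This stands as far as it goes. A reader might infer that related bleeds will certainly be dropped, and the documents do not support that. But if the bleeds are tabulated, the tables contradict the definition in SAP 9.1. Two analysts could each defend a different primary safety table from the same data, and the SAP does not say which is right.

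A second reply is that bleeding episodes may mean hemophilia bleeds only, much as protocol 8.3.6 uses the term when it sets the default. A reader might infer that the SAP clearly excludes bleeding from other causes, but on this narrower reading such bleeding falls outside the sentence and no conflict is shown. SAP text between 7.2.1 and section 9 is redacted and could hold a definition. This reading does not bring back the related or worse-than-expected conditions, so rows 3 and 4 of the comparison are unaffected.

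A third reply is that the study is descriptive and bleeds are reported elsewhere, in Table 14.2.2.1 and the bleeding figures. That limits the consequence. Judging by their titles, however, those outputs summarise bleeding frequency and do not replace tabulation by relatedness or severity.

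**Conclusion.** The contradiction is real, sits in unredacted text and bears on a primary endpoint. It should be corrected before database lock, the point by which protocol 9.4 requires the SAP to be final.

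Its reach is narrow. Serious bleeds are kept under both documents. A reader might infer that the omitted bleeds are exactly the drug-related ones. They are not: worse-than-expected bleeds judged unrelated are omitted too, and they affect only the overall TEAE tables. A reader might also take 1/n as the loss for every participant with an omitted bleed. It applies only where that bleed is the participant's sole drug-related TEAE. The relevant n is the dose group, so the loss can reach 20 points in a group of five.

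The conclusion assumes that the SAP 9.1 sentence is applied as written and that no redacted SAP text restores the missing conditions. The number of bleeds affected is unknown.

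The likely cause, as an inference only, is that the SAP was not fully updated to the current protocol. SAP 9.1.4, for example, cites the toxicity scale as Appendix A3, whereas it is now protocol Appendix 8.

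**What to change.** Replace the bleed sentence in SAP 9.1 with the rule in protocol 8.3.6, and add that:

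- every bleed recorded as an AE under that section, including bleeding not due to hemophilia, enters the TEAE, relationship, severity and toxicity-grade tables, subject to the usual treatment-emergent rule;
- hemophilia bleeds that meet none of the conditions are analysed only as bleeding episodes.

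The cost is one or two sentences in the SAP. The protocol already requires sites to record these events, so no new data and no design change are needed.
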